3.2. Schema

Figure 1: Opioid Taper

Standard Study Schedule

^a Subjects experiencing intolerable opioid withdrawal symptoms may pause the opioid taper, as described in Section 9.3. An opioid taper pause includes either a return to the last stable opioid dose for the remainder of the current opioid dose reduction period (eg, if a subject experiences intolerable withdrawal at the second reduction stage [25% of baseline MED], they can return to the first reduction dose [50% of baseline MED]), or remaining on the current opioid dose instead of reducing at the next scheduled reduction, resulting in an overall extended opioid taper period and study duration.

20

3.3. Schedule of Assessments

	Screen	ing ^a					Stu	dy Dru	g Admi	inistra	tion ^b						Safe	ety Follov	v-up	
Method	Screening	RC	Visit 1	PC 1	Visit 2	RC		PC 2	Visit 3	RC		PC 3	Visit 4	RC	PC 4	Visit 5	PC 5	EOS	PCs 6,7,8	30-day PC 9
Timing	Days -28 to -2	Day -1	Day 1	Day 2	Day 3	Day 5	Day 6	Day 7	Day 8	Day 12	Day 13	Day 14	Day 15	Day 17	Days 18-21	Day 22	Days 23-27	Day 28	Days 29-50	Follow -up ^c
Visit window					±1 day				±1 day				±1 day			±1 day		±1 day		
Informed consent and HIPAA authorization																				
Inclusion/exclusion	X																			
Demographics	Х																			
Medical history	Х		update																	
Record Pain Management Plan	Х							Updates	s should	l be caj	otured t	hrough	out the	study						
Characterize Baseline pain condition	Х																			
Characterize opioid use and opioid withdrawal history ^d	Х																			
MINI	Х																			
Randomization			Х																	
Complete PE	X																			
Brief PE			Х		Х				Х				X			Х		Х		
Height	X																			
Weight	X																	X		
Urine pregnancy test ^e	X																	X		
Urine test for opioids	X		Х		Х				Х				Х			Х		Х		
Urine drug screen for illicit substances ^f	Х		X		Х				Х				X			Х		Х		

Table 2:Schedule of Assessments Performed at the Clinic and Phone Calls: Standard Study Schedule

	Screen	ing ^a					Stu	dy Dru	g Admi	inistra	tion ^b						Safe	ety Follow	v-up	
Method	Screening	RC	Visit 1	PC 1	Visit 2	RC		PC 2	Visit 3	RC		PC 3	Visit 4	RC	PC 4	Visit 5	PC 5	EOS	PCs 6,7,8	30-day PC 9
Timing	Days -28 to -2	Day -1	Day 1	Day 2	Day 3	Day 5	Day 6	Day 7	Day 8	Day 12	Day 13	Day 14	Day 15	Day 17	Days 18-21	Day 22	Days 23-27	Day 28	Days 29-50	Follow -up ^c
Visit window					±1 day				±1 day				±1 day			±1 day		±1 day		
Urine test for alcohol ^g	X		Х		Х				Х				Х			Х		Х		
Clinical chemistry	Х												Х					Х		
Hematology	Х																			
Urinalysis	Х																			
Vital signs ^h	Х		X	Х	Х			Х	Х			Х	Х			Х		Х		
Electrocardiogram	Х		Х		Х				Х				Х			Х		Х		
COWS			Х		Х				Х				Х			Х		Х		
SOWS-H and SOWS-Gossop			x		Х				Х				X			Х		Х		
MCGI-S					Х				Х				Х			Х		Х		
MCGI-R					Х				Х				Х			Х		Х		
NRS chronic pain scales	Х		Х		Х				Х				Х			Х		Х		Х
NRS all over body pain scales			x		Х				Х				Х			Х		Х		
EQ-5D-5L	Х																	Х		
SF-36	Х							I				I						Х		
ISI	Х												Х					Х		
HADS	Х							I				I						Х		
C-SSRS ⁱ	Х		Х		Х				Х				Х			Х		Х		
Dispense diary	Х																			

	Screen	ing ^a					Stu	dy Dru	g Admi	inistra	tion ^b						Safe	ety Follow	v-up	
Method	Screening	RC	Visit 1	PC 1	Visit 2	RC		PC 2	Visit 3	RC		PC 3	Visit 4	RC	PC 4	Visit 5	PC 5	EOS	PCs 6,7,8	30-day PC 9
Timing	Days -28 to -2	Day -1	Day 1	Day 2	Day 3	Day 5	Day 6	Day 7	Day 8	Day 12	Day 13	Day 14	Day 15	Day 17	Days 18-21	Day 22	Days 23-27	Day 28	Days 29-50	Follow -up ^c
Visit window					±1 day				±1 day				±1 day			±1 day		±1 day		
Diary review and check compliance			x		Х				х				х			Х		Х		
Phone call ^j				Х				Х				Х			X ^k		$\mathbf{X}^{\mathbf{l}}$		X ^m	Х
Reminder contact ⁿ		Х				Х				Х				Х						
Opioid dose reduction ^o		Х					х				Х									
Return study drug					Х				Х				Х			Х				
Dispense/re-dispense study drug			X		Х				Х				X							
Study drug dosing ^p							Contin	uously	as direc	ted in j	orotoco	1								
Subject satisfaction																		Х		
Subject interview ^q																		Х		
Opioid compliance			Х		Х				Х				Х			Х		Х		
Subject training – Reporting of pain and opioid withdrawal symptoms	x					Traiı	ning sh	ould be	repeate	ed or re	inforce	d if nec	essary							
Subject training – Vital signs ^r			Х	Trair	ning sho	ould be	repeate	ed if sub	oject ha		using pliance		nitor or	demon	strates	lack of p	rotocol			
Subject training – At home diary completion ^s	x			Tra	ining sl	nould b	e repea	ited if s	ubject d	lemons	trates la	ack of p	orotocol	compl	iance					
AEs			Х	Х	Х			Х	Х			Х	Х		Х	Х	Х	Х	Х	Х

	Screen	ning ^a					Stu	dy Dru	g Adm	inistra	tion ^b						Safe	ty Follow	v-up	
Method	Screening	RC	Visit 1	PC 1	Visit 2	RC		PC 2	Visit 3	RC		PC 3	Visit 4	RC	PC 4	Visit 5	PC 5	EOS	PCs 6,7,8	30-day PC 9
Timing	Days -28 to -2	Day -1	Day 1	Day 2	Day 3	Day 5	Day 6	Day 7	Day 8	Day 12	Day 13	Day 14	Day 15	Day 17	Days 18-21	Day 22	Days 23-27	Day 28	Days 29-50	Follow -up ^c
Visit window					±1 day				±1 day				±1 day			±1 day		±1 day		
Prior and concomitant treatments	x		х		х				х				х			Х		Х		х

AE = adverse event; COWS = Clinical Opiate Withdrawal Scale; C-SSRS = Columbia-Suicide Severity Rating Scale; EOS = end of study; EQ-5D-5L = EuroQol 5-Dimension 5-Level; HADS = Hospital Anxiety and Depression Scale; HIPAA = Heath Insurance Portability and Accountability Act; ISI = Insomnia Severity Index; MCGI-R = Modified Clinical Global Impression – Rater Version; MCGI-S = Modified Clinical Global Impression – Subject Version; MED = morphine equivalent dose; MINI = Mini-International Neuropsychiatric Interview; PC = phone call; PE = physical examination; RC = reminder contact; SF-36 = Short Form Health Survey – 36 items; SOWS-Gossop = Short Opiate Withdrawal Scale of Gossop; SOWS-H = Subjective Opiate Withdrawal Scale of Handelsman

^a The Screening Visit may be conducted over the course of multiple visits, as needed.

^b Subjects who experience intolerable withdrawal symptoms may temporarily suspend the opioid taper once (Section 9.3). See study drug taper schedule in Section 9.2.3.

^c Phone call 30 days after the last dose of study drug. See Table 4 for other assessments to be captured during the phone call, in addition to follow-up on any outstanding AEs or concomitant treatment usage.

^d The subject's baseline opioid use and changes to doses for planned taper reductions should be submitted to and approved by the Medical Monitor prior to Day -1.

^e All female subjects, regardless of childbearing potential.

^f Confirmatory quantitative testing for illicit substances identified in qualitative testing results may be performed.

^g Subjects should refrain from alcohol consumption during the study. Repeated alcohol use (eg, 2 positive tests for alcohol after Screening) during the study requires subject discontinuation.

^h On Day 1, orthostatic vital signs should be assessed pre-dose and 1-hour post-dose of study drug. A post-dose assessment is not required after Day 1 at clinic visits. During phone calls, at-home vital signs (systolic and diastolic blood pressure and pulse) should be recorded after the subject rest for at least 5 minutes.

ⁱ Baseline version at Screening and 'Since Last Visit' version at subsequent visits.

^j Phone calls will include review of an at-home vital signs assessment by the subject, an assessment of how the subject is feeling, and review of any changes to study drug dosing.

- ^k Phone call will take place on Day 19, to check on the subject's well-being and to assess how the subject is feeling.
- ¹ Phone call will take place on Day 25, to check on the subject's well-being and to assess how the subject is feeling.
- ^m Phone calls will take place on Days 32, 39, and 46, to check on the subject's well-being and to assess how the subject is feeling.
- ⁿ Reminders contacts may be done via phone, text, or other electronic message. Remind the subjects about opioid dose reductions or, at Day 17, study drug dose reductions.
- Opioid dose will be decreased 50% from baseline MED beginning with the last dose of the day on Day -1, an additional 25% of baseline MED beginning on Day 6, and a final 25% (to dose of zero) beginning on Day 13. Opioid dose reduction may not occur on a Friday or Saturday unless the clinic can accommodate

subjects on Saturday and Sunday. Subjects who experience intolerable withdrawal symptoms despite increasing their dose of study drug to the maximum tolerated dose will be allowed to pause the opioid taper once. See Table 3 for the opioid taper schedule for subjects who must pause the taper.

- ^p Detailed study drug dosing information can be found in Section 9.2.3. Study drug taper begins on Day 18.
- ^q Subject interview will be conducted via a centralized interviewer through a phone call. The interview should take place no more than 5 days after the EOS Visit.
- ^r Training includes when to call the site due to symptoms of hypertension or hypotension, or if the subject records a vital signs measurement that meets the criteria to contact the site.
- ^s Training includes recording all pharmacologic and non-pharmacologic concomitant treatments (including opioid medications), study drug dose administration, scale assessments for both pain (Average Daily and Worst Daily NRS) and opioid withdrawal scales (SOWS-Gossop, SOWS-Handelsman, and MCGI-Subject), and recording of at-home vital signs (during study drug taper and through EOS only).

	Screeni	ing ^a							Study 1	Drug	Admi	nistra	tion ^b									Safety I	Follow-ı	ap
Method	Screenin g	RC	Visit 1	PC 1	Visit 2	RC		PC 2	Visit 3	RC		PC 3	Visit 4	RC		PC 3P	Visit 4P	RC	PC 4	Visit 5	PC 5	EOS	PCs 6,7,8	30-day PC 9
Timing	Days -28 to -2	Day -1	Day 1	Day 2	Day 3	Day 5	Day 6	Day 7	Day 8	Day 12	Day 13	Day 14	Day 15	Day 18	Day 19	Day 20	Day 21	Day 23	Days 24- 27	Day 28	Days 29- 33	Day 34		Follow -up ^c
Visit window					±1 day				±1 day				±1 day				±1 day			±1 day		±1 day		
Informed consent and HIPAA authorization	Х																							
Inclusion/exclusio n	Х																							
Demographics	Х																							
Medical history	Х		updat e																					
Record Pain Management Plan	Х				•				Upd	ates sł	nould	be cap	tured t	hroug	hout	the stu	ıdy		I	•				
Characterize Baseline pain condition	Х																							
Characterize opioid use and opioid withdrawal history ^d	Х																							
MINI	Х																							
Randomization			Х																					
Complete PE	Х																							
Brief PE			Х		Х				Х				Х				Х			Х		Х		
Height	Х																							
Weight	Х																					Х		

Table 3:Schedule of Assessments Performed at the Clinic and Phone Calls: Study Schedule with Opioid Taper Pause

	Screen	ing ^a							Study]	Drug	Admi	nistra	tion ^b									Safety I	Follow-	սթ
Method	Screenin g	RC	Visit 1		Visit 2	RC		PC 2	Visit 3	RC		PC 3	Visit 4	RC		PC 3P	Visit 4P	RC	PC 4	Visit 5	PC 5	EOS	PCs 6,7,8	30-day PC 9
Timing	Days -28 to -2	Day -1	Day 1	Day 2	Day 3	Day 5	Day 6	Day 7	Day 8	Day 12	Day 13	Day 14	Day 15	Day 18	Day 19	Day 20	Day 21	Day 23	Days 24- 27	Day 28	Days 29- 33	Day 34	Days 35-56	Follow -up ^c
Visit window					±1 day				±1 day				±1 day				±1 day			±1 day		±1 day		
Urine pregnancy test ^e	Х																					Х		
Urine test for opioids	Х		X		x				Х				Х				Х			Х		Х		
Urine drug screen for illicit substances ^f	Х		x		х				X				X				X			х		Х		
Urine test for alcohol ^g	Х		Х		x				Х				Х				Х			х		Х		
Clinical chemistry	Х												Х									Х		
Hematology	Х																							
Urinalysis	Х																							
Vital signs ^h	Х		Х	Х	Х			Х	Х			Х	Х			Х	X			Х		Х		
Electrocardiogram	Х		Х		Х				Х				Х				X			Х		Х		
COWS			Х		Х				Х				Х				X			Х		Х		
SOWS-H and SOWS-Gossop			х		X				Х				Х				Х			Х		Х		
MCGI-S					Х				Х				Х				Х			Х		Х		
MCGI-R					X	1			Х				Х			1	Х	1		Х		Х		
NRS chronic pain scales	Х		x		x				Х				Х				х			Х		Х		X
NRS all over body pain scales			х		х				Х				Х				х			Х		Х		
EQ-5D-5L	Х																					Х		

	Screeni	ing ^a							Study]	Drug	Admi	nistra	tion ^b									Safety I	Follow-	սթ
Method	Screenin g	RC	Visit 1		Visit 2	RC		PC 2	Visit 3	RC		PC 3	Visit 4	RC		PC 3P	Visit 4P	RC	PC 4	Visit 5	PC 5	EOS	PCs 6,7,8	30-day PC 9
Timing	Days -28 to -2	Day -1	Day 1	Day 2	Day 3	Day 5	Day 6	Day 7	Day 8	Day 12	Day 13	Day 14	Day 15	Day 18	Day 19	Day 20	Day 21	Day 23	Days 24- 27	Day 28	Days 29- 33	Day 34	Days 35-56	Follow -up ^c
Visit window					±1 day				±1 day				±1 day				±1 day			±1 day		±1 day		
SF-36	Х																					Х		
ISI	Х												Х									Х		
HADS	Х																					Х		
C-SSRS ⁱ	Х		Х		Х				Х				Х				Х			Х		Х		
Dispense diary	Х																							
Diary review and check compliance			х		х				Х				Х				х			х		Х		
Phone call ^j				Х				Х				Х				Х			X ^k		X ¹		X ^m	Х
Reminder contact ⁿ		Х				Х				Х				Х				Х						
Opioid dose reduction ^o		х					x				х				X									
Return study drug					Х				Х				Х				X			X				
Dispense/re- dispense study drug			х		х				х				Х				х							
Study drug dosing ^p				•				Co	ntinuou	isly as	direct	ted in	protoco	ol				•						
Subject satisfaction																						Х		
Subject interview ^q																						Х		
Opioid compliance			х		X				Х				Х				х			Х		Х		

	Screen	ing ^a							Study]	Drug	Admi	nistra	tion ^b									Safety I	Follow-1	սթ
Method	Screenin g	RC	Visit 1	PC 1	Visit 2	RC		PC 2	Visit 3	RC		PC 3	Visit 4	RC		PC 3P	Visit 4P	RC	PC 4	Visit 5	PC 5	EOS	PCs 6,7,8	30-day PC 9
Timing	Days -28 to -2	Day -1	Day 1	Day 2	Day 3	Day 5	Day 6	Day 7	Day 8	Day 12	Day 13	Day 14	Day 15	Day 18	Day 19	Day 20	Day 21	Day 23	Days 24- 27	Day 28	Days 29- 33	Day 34	•	Follow -up ^c
Visit window					±1 day				±1 day				±1 day				±1 day			±1 day		±1 day		
Subject training – Reporting of pain and opioid withdrawal symptoms	х				Training should be repeated or reinforced if necessary																			
Subject training – Vital signs ^r	Х		Х	Train	ing shou	ld be i	repea	ted if	subject	has is	ssues 1	using t	he mor	itor o	r den	nonstra	ates lac	k of j	protoc	ol comp	liance			
Subject training – At home diary completion ^s	х				Training should be repeated if subject has issues using the monitor or demonstrates lack of protocol complian Training should be repeated if subject demonstrates lack of protocol compliance																			
AEs	Х		Х	Х	Х			Х	Х			Х	Х			Х	Х		Х	Х	Х	Х	Х	Х
Prior and concomitant treatments	Х		X		Х				х				Х				Х			Х		Х		X

AE = adverse event; COWS = Clinical Opiate Withdrawal Scale; C-SSRS = Columbia-Suicide Severity Rating Scale; EOS = end of study; EQ-5D-5L = EuroQol 5-Dimension 5-Level; HADS = Hospital Anxiety and Depression Scale; HIPAA = Heath Insurance Portability and Accountability Act; ISI = Insomnia Severity Index; MCGI-R = Modified Clinical Global Impression – Rater Version; MCGI-S = Modified Clinical Global Impression – Subject Version; MED = morphine equivalent dose; MINI = Mini-International Neuropsychiatric Interview; PC = phone call; PE = physical examination; RC = reminder contact; SF-36 = Short Form Health Survey– 36 items; SOWS-Gossop = Short Opiate Withdrawal Scale of Gossop; SOWS-H = Subjective Opiate Withdrawal Scale of Handelsman

^a The Screening Visit may be conducted over the course of multiple visits, as needed.

^b Subjects who experience intolerable withdrawal symptoms may temporarily suspend the opioid taper once (Section 9.3). See study drug taper schedule in Section 9.2.3.

^c Phone call 30 days after the last dose of study drug. See Table 5 for other assessments to be captured during the phone call, in addition to follow-up on any outstanding AEs or concomitant treatment usage.

^d The subject's baseline opioid use and changes to doses for planned taper reductions should be submitted to and approved by the Medical Monitor prior to Day -1.

^e All female subjects, regardless of childbearing potential.

^f Confirmatory quantitative testing for illicit substances identified in qualitative testing results may be performed.

- ^g Subjects should refrain from alcohol consumption during the study. Repeated alcohol use (eg, 2 positive tests for alcohol after Screening) during the study requires subject discontinuation.
- ^h On Day 1, orthostatic vital signs should be assessed pre-dose and 1-hour post-dose of study drug. A post-dose assessment is not required after Day 1 at clinic visits. During phone calls, at-home vital signs (systolic and diastolic blood pressure and pulse) should be recorded after the subject rest for at least 5 minutes.
- ⁱ Baseline version at Screening and 'Since Last Visit' version at subsequent visits.
- ^j Phone calls will include review of an at-home vital signs assessment by the subject, an assessment of how the subject is feeling, and review of any changes to study drug dosing.
- ^k Phone call will take place on Day 25, to check on the subject's well-being and to assess how the subject is feeling.
- ¹ Phone call will take place on Day 31, to check on the subject's well-being and to assess how the subject is feeling.
- ^m Phone calls will take place on Days 38, 45, and 52, to check on the subject's well-being and to assess how the subject is feeling.
- ⁿ Reminders contacts may be done via phone, text, or other electronic message. Remind the subjects about opioid dose reductions or, at Day 24, study drug dose reductions.
- ^o Opioid dose will be decreased 50% from baseline MED beginning with the last dose of the day on Day -1. The opioid dose will be decreased or maintained beginning on Day 6. The opioid dose will be decreased an additional 25% of baseline MED or maintained beginning on Day 13. A final 25% (to dose of zero) reduction will be made beginning on Day 19. Subjects who experience intolerable withdrawal symptoms despite increasing their dose of study drug to the maximum tolerated dose will be allowed to pause the opioid taper once. Pausing the opioid taper includes either a return to the last stable opioid dose for the remainder of the current opioid dose reduction period (eg, if a subject experiences intolerable withdrawal at the second reduction stage [25% of baseline MED], they can return to the first reduction dose [50% of baseline MED]), or remaining on the current opioid dose instead of reducing at the next scheduled reduction, resulting in an overall extended opioid taper period and study duration. In this scenario, a subject will taper to a dose of zero beginning on Day 19. Opioid dose reduction may not occur on a Friday or Saturday unless the clinic can accommodate subjects on Saturday and Sunday.
- ^p Detailed study drug dosing information can be found in Section 9.2.3. Study drug taper begins on Day 24.
- ^q Subject interview will be conducted via a centralized interviewer through a phone call. The interview should take place no more than 5 days after the EOS Visit.
- ^r Training includes when to call the site due to symptoms of hypertension or hypotension, or if the subject records a vital signs measurement that meets the criteria to contact the site.
- ^s Training includes recording all pharmacologic and non-pharmacologic concomitant treatments (including opioid medications), study drug dose administration, scale assessments for both pain (Average Daily and Worst Daily NRS) and opioid withdrawal scales (SOWS-Gossop, SOWS-Handelsman, and MCGI-Subject), and recording of at-home vital signs (during study drug taper and through EOS only).

	Scree	ening								5	Study	Drug	g Adn	ninist	ratio	n ^a								Safety F	'ollow-up
Timing	Days -28 to -2	Day -1	Day 1	Day 2	Day 3	Day 4	Day 5	Day 6	Day 7	Day 8	Day 9	Day 10	Day 11	Day 12	Day 13	Day 14	Day 15	Day 16	Day 17	Day 18	Day 19	Day 20	Day 21	Days 22-27	Follow- up ^b
Site contact ^c		Х		Х			Х		Х					Х		Х			Х		Х			Х	Х
SOWS-H and SOWS-Gossop ^d			Х	Х	Х	Х	Х	Х	Х	Х	Х	Х	Х	Х	Х	Х	Х	Х	Х	Х	Х	Х	Х	Х	
MCGI-S ^d			Х	Х	Х	Х	Х	Х	Х	Х	Х	Х	Х	Х	Х	Х	Х	Х	Х	Х	Х	Х	Х	Х	
NRS chronic pain scales ^{d,e}	Х	Х	Х	Х	Х	Х	Х	Х	Х	Х	Х	Х	Х	Х	Х	Х	Х	Х	Х	Х	Х	Х	Х	Х	X
NRS all over body pain scales ^d			Х	Х	Х	Х	X	Х	Х	Х	Х	Х	Х	Х	Х	Х	Х	Х	Х	Х	Х	Х	Х	Х	
EQ-5D-5L																									Х
Record study drug and concomitant treatment use ^d		Х	X	X	X	X	X	X	X	Х	Х	Х	X	X	Х	X	X	X	X	X	Х	Х	Х	х	
Vital signs – Phone report ^f				Х					Х							Х									
Vital signs – Subject diary ^g																				Х	Х	Х	Х	Х	
AEs				Х					Х							Х									Х

Table 4: Schedule of Assessments Performed at Home: Standard Study Schedule

AE = adverse event; EOS = end of study; EQ-5D-5L = EuroQol 5-Dimension 5-Level; MCGI-S = Modified Clinical Global Impression – Subject Version; NRS = Numeric Rating Scale; SOWS-Gossop = Short Opiate Withdrawal Scale of Gossop; SOWS-H = Subjective Opiate Withdrawal Scale of Handelsman

^a Subjects who experience intolerable withdrawal symptoms may temporarily suspend the opioid taper once (Section 9.3). See study drug taper schedule (Section 9.2.3). See Table 5 for the schedule of assessments to be performed at home for subjects who must pause the taper.

^b Phone call 30 days after the last dose of study drug. Subjects will be asked to report their current opioid dose/regimen and complete several scales (EQ-5D-5L and NRS pain scales) over the phone.

^c Reminder contacts will take place on Days -1, 5, 12, and 17. Phone calls from the clinic staff will take place on Days 2, 7, 14, 25, 32, 39, 46, and 30 days following the last dose of study drug (follow-up phone call). A subject phone interview, conducted by a centralized interviewer, will take place between Days 28 and 33.

^d Completed at home before bedtime.

^e Subjects will continue to complete the NRS chronic pain scales every day between the EOS Visit and the phone call 30 days following the last dose of study drug (follow-up phone call).

^f During the phone call to the subject, the site should ask the subject to collect and report their vital signs. The subject will not record this reading in their diary.

^g Readings will be taken once in the morning and once in the evening and reported in the subject's diary.

	Scree	ning											Stu	ıdy E	Drug	Adn	ninis	trati	i on a												afety low-up
Timing	Days -28 to -2	Day -1		Day 2	Day 3	Day 4	Day 5	Day 6	Day 7	Day 8	Day 9	Day 10	Day 11	Day 12	Day 13				Day 17	Day 18				Day 22	Day 23	Day 24	Day 25			Days 28- 33	Follow- up ^b
Site contact ^c		Х		Х			Х		Х					Х		Х				Х		Х			Х		Х			Х	Х
SOWS-H and SOWS-Gossop ^d			X	х	х	х	Х	х	х	Х	х	х	Х	х	х	Х	х	х	х	Х	х	х	х	х	х	х	х	х	х	Х	
MCGI-S ^d			Х	Х	Х	Х	Х	Х	Х	Х	Х	Х	Х	Х	Х	Х	Х	Х	Х	Х	Х	Х	Х	Х	Х	Х	Х	Х	Х	Х	
NRS chronic pain scales ^{d,e}	Х	Х	х	х	х	х	Х	х	х	Х	х	х	х	х	Х	Х	х	х	х	Х	х	х	х	х	х	х	х	Х	Х	Х	Х
NRS all over body pain scales ^d			Х	х	х	х	Х	х	х	Х	Х	х	х	х	Х	Х	х	х	х	Х	Х	х	х	х	Х	х	х	Х	Х	Х	
EQ-5D-5L																															Х
Record study drug and concomitant treatment use ^d		X	x	x	x	x	х	x	х	х	x	х	x	х	х	х	x	x	x	х	x	х	x	x	x	x	x	Х	Х	Х	
Vital signs – Phone report ^f				х					Х							Х						Х									
Vital signs – Subject diary ^g																										х	х	Х	Х	Х	
AEs				Х					Х							Х						Х									Х

Table 5: Schedule of Assessments Performed at Home: Study Schedule with Opioid Taper Pause

AE = adverse event; EOS = end of study; EQ-5D-5L = EuroQol 5-Dimension 5-Level; MCGI-S = Modified Clinical Global Impression – Subject Version;

NRS = Numeric Rating Scale; SOWS-Gossop = Short Opiate Withdrawal Scale of Gossop; SOWS-H = Subjective Opiate Withdrawal Scale of Handelsman ^a Subjects who experience intolerable withdrawal symptoms may temporarily suspend the opioid taper once (Section 9.3). See study drug taper schedule (Section 9.2.3).

^b Phone call 30 days after the last dose of study drug. Subjects will be asked to report their current opioid dose/regimen and complete several scales (EQ-5D-5L and NRS pain scales) over the phone.

^c Reminder contacts will take place on Days -1, 5, 12, 18, and 23. Phone calls from the clinic staff will take place on Days 2, 7, 14, 20, 25, 31, 38, 45, 52, and 30 days following the last dose of study drug (follow-up phone call). A subject phone interview, conducted by a centralized interviewer, will take place between Days 34 and 39.

^d Completed at home before bedtime.

^e Subjects will continue to complete the NRS chronic pain scales every day between the EOS Visit and the phone call 30 days following the last dose of study drug (follow-up phone call).

^f During the phone call to the subject, the site should ask the subject to collect and report their vital signs. The subject will not record this reading in their diary.

^g Readings will be taken once in the morning and once in the evening and reported in the subject's diary.

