8.6. Early Discontinuation Visit

If a subject is discontinued from the study before completion, regardless of whether they have received study drug, the reason for discontinuation must be documented in the subject's source document and eCRF. Whenever a subject is discontinued, the procedures/assessments listed for the EOS Visit in the Schedule of Assessments (Table 2 or Table 3) should be performed. If a subject discontinues on a scheduled visit, assessments completed at that visit should be entered into the eCRF for that scheduled visit. Assessments required for the EOS Visit that are not required at the scheduled visit (eg, a complete physical examination, clinical laboratory tests) should be completed and entered into the eCRF for the EOS Visit.

Subjects who prematurely discontinue the study will be instructed to taper study drug as described in Section 9.2.3 and to complete the at-home assessments for the study drug taper period (Table 4 or Table 5). Once discontinued, subjects may not re-enter the study.

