8.6.1. Early Discontinuation Follow-up

If a subject discontinues from the study, the subject will be contacted 30 days after the last day of study drug administration, unless the subject withdraws consent and refuses post-study contact. This telephone contact will be recorded in the source document. If a subject discontinues participation due to an AE/SAE that is at least possibly related to study drug, the subject will be followed until the event has resolved, stabilized or otherwise explained.

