Dosing of study drug will continue for 5 days after the last opioid dose. Study drug will then be tapered over an additional 4 days. The following schedule will be followed over the study drug taper period:

- If taking 4 tablets QID (LUCEMYRA 2.88 mg/day or matching placebo) on fifth day after the last opioid dose
 - 3 tablets QID (LUCEMYRA 2.16 mg/day or matching placebo) for 1 day

- 2 tablets QID (LUCEMYRA 1.44 mg/day or matching placebo) for 2 days
- 1 tablet QID (LUCEMYRA 0.72 mg/day or matching placebo) for 1 day
- Study drug discontinued
- If taking 3 tablets QID (LUCEMYRA 2.16 mg/day or matching placebo) on fifth day after the last opioid dose
 - 2 tablets QID (LUCEMYRA 1.44 mg/day or matching placebo) for 2 days
 - 1 tablet QID (LUCEMYRA 0.72 mg/day or matching placebo) for 2 days
 - Study drug discontinued
- If taking 2 tablets QID (LUCEMYRA 1.44 mg/day or matching placebo) on fifth day after the last opioid dose
 - 1 tablet QID (LUCEMYRA 0.72 mg/day or matching placebo) for 2 days
 - 1 tablet twice daily (LUCEMYRA 0.36 mg/day or matching placebo) for 2 days
 - Study drug discontinued
- If taking 1 tablet QID (LUCEMYRA 0.72 mg/day or matching placebo) on the fifth day after the last opioid dose
 - 1 tablet twice daily (LUCEMYRA 0.36 mg/day or matching placebo) for 4 days
 - Study drug discontinued

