12.2.3. Recording Adverse Events

All AEs and details for the events will be recorded in the subject's source document and eCRF. An AE should be documented in terms of a medical diagnosis and reported in standard medical terminology when possible. When this is not possible, the AE should be documented in terms of signs and/or symptoms observed or reported. It is important for the Investigator to only record 1 AE per line on the eCRF. Combination events (eg, nausea/vomiting), should be entered as 2 events.

The Investigator must determine the intensity of the AE as defined by:

- Mild: no medical interventions required, short lasting discomfort, and does not interfere with subject's daily activities
- Moderate: activity may be limited, and subject may require minimal medical therapy, intervention, or assistance
- Severe: definitely limits subject's daily activity that may require hospitalization and or intervention/therapy assess whether or not the study drug caused the AE

The Investigator will record whether the AE or AEs led to discontinuation of the subject from the study, record the outcome of the AE (unresolved, resolved, resolved with sequelae, death, or unknown), and determine if the AE is serious.

For this study, AEs and SAEs will be collected beginning with the start of dosing on Day 1 and will end 30 days after the last dose of study drug.

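### Completers have seven scheduled adverse-event contacts in the 30 days after the last dose and early discontinuers one or two, so between-arm TEAE percentages could be biased if dropout differs by arm

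*Combined protocol and SAP*

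**What the plan says.** The AE collection window is the same for everyone. It opens at the first dose and, under Section 12.2.3, "will end 30 days after the last dose of study drug".

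For subjects who finish, Section 3.3 fixes the follow-up by study day. In Table 2 the AE row is marked at Visit 5, PC 5, the EOS visit, PCs 6 to 8 and PC 9. The footnotes date the calls: "Phone call will take place on Day 25, to check on the subject's well-being" (PC 5) and "Phone calls will take place on Days 32, 39, and 46, to check on the subject's well-being" (PCs 6 to 8). PC 9 falls 30 days after the last dose. Table 3 repeats the pattern for subjects who pause the opioid taper.

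For subjects who stop early, Section 8.6 says that "the procedures/assessments listed for the EOS Visit in the Schedule of Assessments (Table 2 or Table 3) should be performed". It also has them taper study drug and complete the at-home assessments for the drug-taper period. Section 8.6.1 then says that "the subject will be contacted 30 days after the last day of study drug administration". No section assigns PCs 5 to 8 to these subjects, and none excludes them. The AE rows of Tables 4 and 5 have no mark in the drug-taper period.

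On the exit examination, Section 8.6 gives as examples of EOS assessments "eg, a complete physical examination, clinical laboratory tests", whereas Tables 2 and 3 mark only a brief physical examination at EOS.

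**The concern.** Safety and tolerability are the primary objective (Section 6.1), and TEAE incidence by arm is one of the endpoints under it. AEs are elicited by an open question about how the subject has felt since the last contact (Section 12.2). A completer answers that question at gaps of 3 to 7 days after the last dose. An early discontinuer may answer it once, for a whole month. New events that are mild or short-lived are the ones such a recall is most likely to lose.

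Measured events are affected too. Completers have clinic vital signs and an ECG at about 1 and 7 days after the last dose, chemistry at about 7 days, and twice-daily home blood pressure through EOS. Discontinuers have the clinic tests at the exit visit and home readings for the drug-taper period. Section 12.1.2 records confirmed readings that meet the hypertension criteria as AEs even without symptoms, and the study rationale names rebound hypertension as a signal to look for.

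If more subjects leave one arm than the other, that arm has more of its follow-up on the sparse schedule and could look safer than it is. Section 8.5 lists reasons for leaving that could plausibly differ by arm (intolerable AEs, cardiovascular events, inability to continue the opioid taper), and Section 13.4.1.4 plans a between-arm test of time to drug discontinuation.

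**Working it through.** **1. Last dose.** Table 2: "Study drug taper begins on Day 18". Section 9.2.3: "Study drug will then be tapered over an additional 4 days". The nominal last dose is therefore Day 21. On the pause schedule the drug taper starts on Day 24, so it is Day 27.

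**2. Completers' AE-marked contacts after the last dose.** Offset = contact day − last-dose day.

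| Contact | Standard day | Pause day | Offset |
|---|---|---|---|
| Visit 5 | 22 | 28 | +1 |
| PC 5 | 25 | 31 | +4 |
| EOS | 28 | 34 | +7 |
| PC 6 | 32 | 38 | +11 |
| PC 7 | 39 | 45 | +18 |
| PC 8 | 46 | 52 | +25 |
| PC 9 | 51 | 57 | +30 |

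That is seven on both schedules. Offsets are nominal; Visit 5 and EOS each have a window of ±1 day.

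**3. Early discontinuers' contacts after the last dose.** The day-30 call is one. The exit visit adds a second only if it takes place after the drug taper; Section 8.6 does not fix the order. The comparison is 7 with 1 or 2, apart from follow-up of events already known.

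**4. The plan's precision figure.** Section 13.2 gives ±0.24 at 20 per group and ±0.17 at 40 per group for a difference of 0.2. It does not state the two proportions; 0.10 and 0.30 (assumed) reproduce both figures. Half-width = 1.96 × √[(0.10 × 0.90 + 0.30 × 0.70)/n] = 1.96 × √(0.30/n):

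- n = 20: 0.240
- n = 40: 0.170
- n = 30 (the planned size): 0.196, or 0.229 after adding the continuity correction of 1/30 = 0.033

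**5. Size of a possible bias.** The documents give none of these inputs; all are assumptions:

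- q = 0.30: share of subjects, equal in both arms, whose first TEAE starts after the last dose
- s = 0.50 to 0.80: capture in discontinuers relative to completers
- d: dropout in each arm

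Observed rate = q × [1 − d × (1 − s)].

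| Dropout by arm | s | Observed rates | Spurious difference |
|---|---|---|---|
| 20% vs 50% | 0.50 | 27.0% vs 22.5% | 4.5 points |
| 20% vs 50% | 0.80 | 28.8% vs 27.0% | 1.8 points |
| 30% vs 40% | 0.50 | 25.5% vs 24.0% | 1.5 points |
| 30% vs 40% | 0.80 | 28.2% vs 27.6% | 0.6 points |

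The difference equals q × (1 − s) × (dropout gap), so it is zero when dropout is equal or s = 1. Over a wider grid (q 0.1 to 0.5, s 0.5 to 1.0, gap 10 to 40 points) it runs from 0 to 0.5 × 0.5 × 0.40 = 10 points.

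**The case against.** A good deal of the case on the other side stands.

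- **Known events are followed.** A reader of Section 8.6.1 alone might infer that only subjects who left for a related AE are followed further. Section 12.2.4 has each AE followed until it resolves, stabilizes or is judged not due to the drug or participation, and Section 12.1.7.1 follows every subject with raised liver tests. It would therefore be wrong to say that every discontinuer goes 30 days without contact. But this follow-up tracks events already recorded; it does not schedule a search for new ones.
- **The window is equal.** The day-30 question reaches back to the last contact, so the risk is poorer recall, not a closed window. The exit visit includes an AE assessment. The drug-taper diary includes vital signs and a daily side-effect rating, and subjects are told to call with symptoms of hypotension, bradycardia or hypertension. These narrow the gap without closing it.
- **A shortfall is not established.** A reader might infer that TEAEs are under-counted in the arm with more dropout. The documents give no dropout rate by arm and no recall data, so that can only be a conditional statement.
- **Counting limits the effect.** Section 13.4.2.1.1 counts a subject once per preferred term, so only a first event of that term starting after the last dose can be lost. A reader might also take TEAE incidence as the single primary outcome; no single one is named, and laboratory tests, vital signs and C-SSRS stand beside it.
- **The effect is small beside the noise.** 4.5 points is 1.35 subjects in 30, and Section 13.4.2 makes safety summaries descriptive. This limits the seriousness but does not justify an avoidable difference in ascertainment.
- **The examination mismatch may cut the other way.** If discontinuers had the complete examination and completers the brief one, more AEs would be found in discontinuers. It is a separate inconsistency and does not support the contact-count argument.

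**Conclusion.** The asymmetry is real and follows from the plan's own schedule: seven scheduled AE contacts after the last dose against one or two. New post-dose TEAEs, especially mild, transient or asymptomatic ones, may be captured less completely in early discontinuers. This becomes a between-arm bias only if dropout differs by arm and detection falls with fewer contacts. Under the stated assumptions the bias is 0.6 to 4.5 points, against a half-width of about 20 points at 30 per group (itself resting on assumed proportions of 0.10 and 0.30). The direction cannot be predicted, because the documents do not show which arm would lose more subjects. The point is worth correcting because it bears on the primary safety objective and is cheap to remove; it does not invalidate the safety comparison.

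**What to change.** In Section 8.6.1 and the call footnotes of Tables 2 and 3 (k to m), time the existing follow-up calls from the last dose instead of by study day, and apply them, with the same AE question, to every dosed subject who has not refused contact. Using the plan's own pattern, a discontinuer would have one call during the drug taper and calls at 4, 11, 18, 25 and 30 days after the last dose.

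The day-30 call already exists, so the cost is up to five short calls per discontinuer by existing site staff, plus a wording change. Some who withdraw consent will decline. The calls even out the questioning; they do not replace the clinic measurements that completers have after the last dose, so some difference in asymptomatic findings would remain.

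Separately, make Section 8.6 agree with Tables 2 and 3 on which physical examination is done at EOS, because clinically significant findings after dosing are recorded as AEs (Section 12.1.4). That is a wording change only.
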